sEH activity and EETs: We will measure sEH activity in two ways. In tissue extracts, we will measure the rate of conversion of an added concentration of 14,15-EET (50 µM) to 14,15-DHET,75 as well as the ratio of DiHOMEs to EpOMEs. The former is a true measure of enzyme activity, and we will compare the DiHOME/EpOME ratio to this gold standard. In plasma we will measure the molar ratio of DiHOME to EpOME. Plasma EETs, DHETs, EpOME, **DiHOMEs** will be quantified using ultra-performance chromatography/tandem mass spectrometry (UPLC/MS/MS).²⁸ Deuterated internal standards (Cayman Chemical, Ann Arbor, MI) will be added to each sample. For lipid extraction, three mL 0.15M KCl will be added to one mL plasma and extracted with eight mL of an acidified chloroform/methanol mixture at a two:one ratio. The organic phase will be collected and saponified (0.4M KOH in 80% methanol). EETs, EpOMEs, DHETs, and DiHOMEs will be separated by SiO₂ chromatography. SiO₂-purified EETs and EpOMEs will be hydrated to DHETs and DiHOMEs, respectively, in 9.5M acetic acid. EETs, EpOMEs, DHETs, and DiHOMEs will be analyzed by UPLC/MS/MS. The UPLC is equipped with an Acquity BEH C18 column 1.0 x 100 mm, 1.7 µm (Waters). To separate analytes, we will perform gradient elution starting with a 70% mobile phase A (15 mM ammonium acetate, pH 8.5) proceeding to a 60% mobile phase B (acetonitrile) over five min. Following gradient elution, columns will be washed for one minute with mobile phase B. The UPLC effluent will then be subjected to negative ion electrospray ionization using a triple quadrupole mass spectrometer, TSQ Quantum Vantage (Thermo Scientific, Hudson, NH), equipped with an electrospray source operating in negative ion-mode. Analytes and internal standards will be monitored using selected reaction monitoring.

Glucose, C-peptide, and Insulin: Plasma glucose will be measured by the glucose oxidase method with a YSI glucose analyzer (YSI Life Sciences, Yellow Springs, OH). 6,6-dideuterated glucose will be assessed using mass spectrometry. Plasma insulin concentrations will be determined by radioimmunoassay (RIA; Millipore, St. Charles, MO). Samples for C-peptide will be drawn into heparinized tubes containing 250 KIU Trasylol (Aprotinin) per mL of whole blood. C-peptide will be measured using RIA (Millipore).

Western blot analysis of pAKT/AKT, CD31, VEGF: Adipose and muscle samples will be homogenized in the presence of proteases and phosphatase inhibitors. For adipose tissue, homogenate will be centrifuged for 10 min at 10,000 g; the stromal vascular fraction from the pellet at will be recovered and the adipocyte fraction (top of the tube) will be used for Western blots. Homogenates will be denatured after mixing with Laemmli buffer and heated at 95°C for 5 min. Samples (30 µg of protein) will be resolved electrophoretically in 4-20% acrylamide gel and transferred to polyvinylidene difluoride membranes (Immobilon-FL, Millipore, Billerica, MA). Membranes will be blocked with Odyssey® blocking buffer and incubated overnight with antibodies: rabbit monoclonal antibody phospho-AKT, total AKT, (Cell Signaling, Danvers, MA), mouse monoclonal against CD31 (ThermoFisher Scientific, Rockland, IL), or mouse monoclonal against VEGF (Novus Biologicals, Littleton, CO). Membranes will then be incubated for one hour with Alexa Fluor 680-conjugated goat antirabbit IgG (Invitrogen, Carlsbad, CA) or IRDye® 800CW donkey anti-mouse (LI-COR Biosciences, Lincoln, NE). Membranes used for phospho-AKT will be stripped and re-probed for total AKT to obtain the ratio of pAKT/AKT expression. Odyssey® Infrared Imaging System (LI-COR Biosciences) will be used to detect fluorescence intensity. Band densities will be analyzed using NIH Image J software. Coomassie blue staining will be used as the loading control for other analyses.

Evaluation of PBMC immune cell populations: We will use flow cytometry to assess activated, memory, exhausted, and senescent CD4 and CD8 populations using surface markers CD38, HLA-DR, CD69, CD57, PD1, and CD45RO (as examples), iNKT cells using CD1d tetramer, as well as M1 (CD14+CD16+ with either CD86 or CD36) and M2 (CD163, CD301, and CD206) macrophage polarization.

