Soluble epoxide hydrolase inhibitors are under development in humans. Among the pharmacological inhibitors of soluble epoxide hydrolase tested in rodents, the first to be tested in humans was 1-(1-acetyl-piperidin-4-yl)-3-adamantan-1-yl-urea or AR9281. A study of the effects of AR9281 in patients with hypertension and impaired glucose tolerance (NCT00847899) was completed, but not published. The sEH inhibitor GSK2256294 [(1R,3S)-N-(4-cyano-2-(trifluoromethyl)benzyl)-3-((4-methyl-6-(methylamino)-1,3,5-triazin-2-yl)amino)cyclohexanecarboxamide] has been studied safely in Phase I and II studies. The tmax is 0.5 hrs, and $t_{1/2}$ is 48 hrs. With multiple dosing in overweight smokers, steady-state was achieved within seven days. GSK2256294 10 mg achieved more than 95% inhibition of sEH throughout the dosing interval.

While sEH inhibition may have beneficial cardiovascular and renal effects in T2DM by improving endothelial function, ^{11,29} there could also be adverse consequences of long-term sEH inhibition. In pre-clinical models, EETs increase vascular endothelial growth factor (VEGF), increase proliferation and survival of endothelial cells, and promote angiogenesis, leading to metastasis of existing tumors.⁴² The effect of sEH inhibition on angiogenesis and tumor growth is complex, however. While EETs promote angiogenesis, other fatty acid substrates of sEH, such as the epoxydocosapentaenoic acids (from omega-3 fatty acids) reduce angiogenesis.⁴³ In some models, dual cyclooxygenase and sEH inhibition decreases angiogenesis and tumor growth.⁴⁴ In addition, chronic inflammation contributes to the development of many cancers, and the anti-inflammatory effects of EETs may prevent these. For example, sEH expression is increased in colon cancer; *Ephx2*-null mice are protected against dextran sulfate sodium-induced colitis and colon cancer.⁴⁵ There was no effect of sEH inhibitor GSK2256294 on circulating VEGF in Phase II studies.¹⁸ In this proof-of-concept study, we will treat patients with an sEH inhibitor for one week to avoid any risk of long-term effects.

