4.0 Inclusion/Exclusion Criteria

Inclusion criteria

- 1. Men and women,
- Age 21 to 60 years, and
- 3. Pre-diabetes as defined by
 - a. Fasting plasma glucose 100-125 mg/dL, or
 - b. Two-hour plasma glucose 140-199 mg/dL, or
 - c. HbA1c 5.7-6.4%
- 4. BMI \geq 30 kg/m², inclusive
- 5. For female subjects, the following conditions must be met:
 - a. Postmenopausal status for at least one year, or
 - b. Status-post surgical sterilization, or
 - c. If of childbearing potential, utilization of adequate birth control and willingness to undergo serum β -hcg testing prior to drug treatment and on every study day.

Exclusion criteria

Subjects presenting with any of the following will not be included in the study:

- Diabetes type 1 or type 2, as defined by a fasting plasma glucose of 126 mg/dL or greater, a two-hour plasma glucose of 200 mg/dL or greater, a HbA1c >6.4%, or the use of anti-diabetic medication
- 2. Subjects who have participated in a weight-reduction program during the last six month or whose weight has increased or decreased more than two kg over the preceding six months
- 3. Resistant hypertension, defined as hypertension requiring the administration of more than three anti-hypertensive agents including a diuretic to achieve control
- 4. Use of spironolactone
- 5. Pregnancy or breast-feeding
- 6. Any significant history of smoking, as defined by smoking one pack-year over any cumulative time or smoking any amount within the last ten years
- Any history of cancer including skin cancer, any history of a precancerous lesion, abnormal PSA, or lack of screening adherent to American Cancer Society Guidelines for the Early Detection of Cancer
- 8. Cardiovascular disease such as myocardial infarction within six months prior to enrollment, presence of angina pectoris, significant arrhythmia, congestive heart failure (left ventricular hypertrophy acceptable), deep-vein thrombosis, pulmonary embolism, second- or third-degree heart block, mitral valve stenosis, aortic stenosis, or hypertrophic cardiomyopathy
- 9. Abnormal corrected QT interval on screening ECG (QTc).
- 10. Treatment with anticoagulants
- 11. History of serious neurologic disease such as cerebral hemorrhage, stroke, or

- transient ischemic attack
- 12. History or presence of immunological or hematological disorders
- 13. Diagnosis of asthma requiring regular inhaler use
- 14. Clinically significant gastrointestinal impairment that could interfere with drug absorption

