Subjects will then be randomized within one month of screening using a permuted-block algorithm to treatment with the sEH inhibitor GSK2256294 (10 mg/d) or matching placebo for one week in a double-blind, crossover design study. The Vanderbilt Investigational Drug Service will be responsible for storage, preparation, labeling, and dispensing of medication. GSK is supplying study drug and matching placebo. GSK2256294 has been studied safely in Phase I and II studies. 18 In multiple dosing studies in overweight smokers, steady state was achieved within seven days. The dose of GSK2256294 achieves >95% inhibition of sEH throughout the dosing interval. Subjects will also be provided a weight-maintenance diet containing 150 mmol/day sodium and 80 mmol/day potassium for one day prior to study. On the seventh day of drug treatment, subjects will report to the CRC in the morning after an overnight fast to undergo a hyperinsulinemic-euglycemic clamp. Urine will be collected overnight for 8 hours prior to the study day, and again after clamp completion. On the day of study, we will place IV catheters in both arms. We will obtain an adipose tissue biopsy (Standard Techniques) and optional muscle tissue biopsy if subject consents. We will administer paraminohippurate (PAH, 8 mg/kg) as a loading dose, followed by a 12 mg/min continuous infusion for measurement of renal blood flow. After the subject has been supine for 45 min (and PAH is at steady state), we will measure forearm blood flow (FBF), BP, and

heart rate in triplicate (**Standard Techniques**). We will draw blood for measurement of GSK2256294 concentrations, PAH, plasma EETs, DHETs, EpOME, DiHOME, interleukin 6 (IL-6) and other inflammatory cytokines, adiponectin, VEGF, and potassium. Subjects will then undergo a hyperinsulinemic-euglycemic clamp (see **Standard Techniques**). We will infuse 6,6-dideuterated glucose to assess endogenous glucose appearance (EndoRa) under fasting conditions, and we will assess hepatic insulin sensitivity by the response to low (20mU/m²/min) and high (80mU/m²/min) insulin infusion rates (**Standard Techniques**). At the end of the clamp we will repeat FBF measurements, followed by adipose tissue and optional muscle biopsy. We have experience obtaining biopsies before and at the end of hyperinsulinemic clamps (**Preliminary Studies**). At the end of each study day, we will obtain safety laboratory including CBC with differential, complete metabolic profile, urinalysis, and ECG.

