After completion of the study day, subjects will undergo a seven-week washout from study drug and then receive the opposite drug for one week, while eating the same standardized diet. On the seventh day of treatment they will report to the CRC after an overnight fast and repeat the study day protocol.

Standard Techniques

BP Measurements: During screening, washout, and active treatment outpatient BP will be measured with an aneroid sphygmomanometer (Welch Allyn, Skaneateles Falls, NY), using the appearance and complete disappearance of the Korotokoff sounds (K1 and K5) as systolic blood pressure (SBP) and diastolic blood pressure (DBP). The mean of three seated measurements will be used. During study days, BP will be measured every five min using an automated oscillometric recording device (Dinamap, Critikon, Carlsbad, CA).

Adipose harvest: Adipose tissue will be obtained from the periumbilical area using a TulipTM Medical closed syringe system for lipoaspiration (see Letter of Support). Under aseptic conditions and local lidocaine anesthesia, a small incision is made in the skin. The GEMS Johnnie Snap lock is placed into a 60-cc syringe, the Tulip liposuction cannula with 60-cc syringe attached is inserted at an angle through the incision to below Scarpa's fascia, and suction is applied until the syringe activates the clicker lock. The needle is moved in and out at a rate of approximately 1 Hz without breaking suction with a twisting motion. The sampling continues until approximately 5 g of tissue is removed (approximately 5.5 cc at a specific gravity of 0.918 for human fat). The syringe containing the sample will be taken on ice to the lab where it will be separated into pieces for measurement of sEH activity, DiHOME, EpOME, EETs, DNA and RNA isolation, adipocyte size and number, cytokines, and adipokines.

PBMC harvest: PBMCs will be obtained through the peripheral IV into 3 EDTA tubes for total of 12 milliliters, and transported at room temperature to the lab for processing. Cells will then be passed through a Ficoll-Paque barrier, washed with PBS, and stored in DMSO.

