7.0 Risks

Potential Risks

- Frequent blood draws can lead to anemia.
- 2. Withholding BP medications may result in elevation in BP. We will monitor BP every one to three days after stopping or decreasing these medications. If the BP is too high (see **Protection against risk**) or there are symptoms of high BP, the study will be stopped and prior medications will be restarted.
- 3. Putting a catheter into a vein may cause bleeding, bruising, or infection (uncommon). We will use careful and sterile technique to minimize these side effects.
- 4. Adipose and muscle tissue biopsies may cause bleeding, bruising, pain, or infection (uncommon). Only trained investigators will complete these procedures. We will use sterile technique to minimize the risk of infection, and local anesthesia (lidocaine) will be used to minimize pain. We will monitor subjects for one hour after the biopsies.
- 5. Infusion of glucose may cause hyperglycemia. Symptoms of high blood sugar are hunger, thirst, frequent urination, dry mouth, and dry skin. Blood will be monitored during and for 2 3 hours after clamp completion to ensure blood sugar remains in the normal range. IV glucose may cause irritation of the vein, including redness and pain. We will give the glucose through a bigger vein to decrease this risk.
- 6. Infusion of insulin may cause hypoglycemia. Symptoms of low blood sugar are nausea, extreme hunger, feeling nervous or jittery, cold, clammy, wet skin and/or excessive sweating not caused by exercise, a rapid heartbeat, and numbness or tingling of the fingertips or lips, and trembling. Glucose (dextrose 20%) will be infused during periods of insulin administration, and glucose will be monitored every five min to maintain normal plasma glucose. After study completion, insulin will be stopped, a meal will be given, and intravenous glucose will be tapered. Blood glucose will be monitored for 2-3 hours after the study until it stabilizes within the normal range.
- 7. Eating a controlled diet for one day may be inconvenient.
- 8. GSK2256294 is an investigational drug. To date there are no safety concerns based on Phase I and II trials in humans. There has been skin irritation at the site of ECG lead placement during GSK2256294. There may be risks that we do not know about at this time. There is a theoretical risk that inhibiting sEH and increasing EETs could promote angiogenesis in pre-existing cancer.

Protections against risk

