9.0 Study Withdrawal/Discontinuation

If at any time during the study, a subject develops any symptoms related to study participation that subject will be withdrawn from the study. If, in the opinion of the investigator, a subject is non-compliant, that subject will be withdrawn from the study. Subjects who are withdrawn will be followed until symptoms have resolved.

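### No safety contact is scheduled after the second study day (day 7 of period 2 dosing), so late adverse events are captured incompletely and in a way that depends on treatment order

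*Protocol*

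**What the plan says.** Protocol section 6.0 puts each subject through two one-week dosing periods with seven weeks of washout between them. The study day is fixed within the period: "On the seventh day of drug treatment, subjects will report to the CRC in the morning after an overnight fast". The scheduled safety tests are tied to it: "At the end of each study day, we will obtain safety laboratory including CBC with differential, complete metabolic profile, urinalysis, and ECG". For period 2 the text reads "On the seventh day of treatment they will report to the CRC after an overnight fast and repeat the study day protocol", and the schedule ends there.

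Other provisions bear on safety follow-up:

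- **Half-life (section 1.0):** "The tmax is 0.5 hrs, and $t_{1/2}$ is 48 hrs".
- **Blood pressure (section 6.0, Standard Techniques):** outpatient readings in screening, washout and active treatment, with no interval given there and nothing after period 2.
- **After procedures (section 7.0):** one hour of observation after biopsies and two to three hours of glucose checks after the clamp.
- **Questionnaire (section 7.0, Protections against risk, item 7):** active adverse event monitoring, with no time points and no end date.
- **Withdrawn subjects (section 9.0):** "Subjects who are withdrawn will be followed until symptoms have resolved". There is no matching provision for subjects who complete.
- **Pregnancy (section 4.0):** women of childbearing potential use adequate birth control and accept serum β-hCG "testing prior to drug treatment and on every study day". Nothing is said about the time after period 2.
- **Section 11.0**, despite the word Follow-up in its title, deals only with keeping records.

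**The concern.** The last safety check in each period falls while the drug is close to its highest level in the body. After period 1 this matters less, because subjects return. After period 2 no scheduled contact would bring a late reaction, a biopsy-site infection or an exposed pregnancy to the investigator's attention. Section 8.0 sets a reporting deadline for serious events that runs from the investigator's notification, but after the last visit nothing scheduled would produce that notification.

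The gap also depends on treatment order. The same late event on active drug has some chance of being recorded in a subject who took active drug first, and must be volunteered by one who took it second. The drug is investigational and section 7.0 accepts that it may carry unknown risks, so what is at stake is the completeness of a small safety record.

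**Working it through.** **1. The plan's own interval.** Seven weeks of washout plus one week on the second treatment gives 7 + 1 = 8 weeks between study days. This reproduces the eight-week period in the SAP's Data Analysis Plan. In half-lives, the washout is 49 d ÷ 2 d = 24.5 and the interval between study days is 56 d ÷ 2 d = 28.

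**2. Where day 7 sits.** Seven days is 7 ÷ 2 = 3.5 half-lives. The fraction of steady state reached is 1 − 2^(−3.5) = 0.91.

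**3. Exposure still to come at the check.** Assume seven equal daily doses, rapid absorption and first-order elimination. The amount in the body *h* hours after the seventh dose, in units of one dose, is

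A(h) = Σ 2^(−(h + 24k)/48), for k = 0 to 6.

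Future AUC is proportional to A(h) and total AUC to 7 doses, so the share to come is A(h)/7. The documents do not give the time from dose to safety check, so a range is shown.

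| Hours after 7th dose | Doses in body | Share of total AUC to come |
|---|---|---|
| 0 | 3.11 | 44% |
| 4 | 2.94 | 42% |
| 8 | 2.77 | 40% |
| 12 | 2.62 | 37% |
| 24 | 2.20 | 31% |

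**4. Decline after the last dose.** Of the amount then present, 2^(−t/48 h) remains: 71% at 1 day, 50% at 2 days, 8.8% at 7 days, 3.1% at 10 days and 0.8% at 14 days.

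**5. What each order has scheduled after each treatment.**

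| | Active first | Active second |
|---|---|---|
| After active drug | Washout blood pressure; one laboratory/ECG eight weeks later, on day 7 of placebo | Nothing after the study day |
| After placebo | Nothing after the study day | Washout blood pressure; one laboratory/ECG eight weeks later, on day 7 of active drug |

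With 34 subjects and 1:1 order (assumed; section 5.0 states only permuted blocks), each column holds 34 ÷ 2 = 17.

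**6. What that does to the safety record.** Suppose a late event can be found only in subjects with a scheduled check after active drug. With no events seen, the one-sided 95% upper limit for the risk is 1 − 0.05^(1/n): 16.2% for n = 17 and 8.4% for n = 34. The chance of seeing at least one event with a true risk of 5% is 1 − 0.95^n: 58% for n = 17 and 83% for n = 34.

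**The case against.** A check at 91% of steady state is well timed for concentration-related effects, and exposure was deliberately limited to one week. The questionnaire has no stated end, the monitoring committee reviews all serious events, and subjects withdrawn for symptoms are followed. All of this stands. It means a reader should not infer that subjects who take active drug second are never observed after exposure. What the documents support is that no assessment is scheduled after their day-7 visit. An open-ended questionnaire with no time points is not a scheduled check, and a completer whose symptoms begin after the last visit is outside section 9.0.

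A reader might also infer that the drug-versus-placebo comparison of adverse events is biased. The table in step 5 shows otherwise. With equal numbers per order, active drug and placebo each have 17 long and 17 short windows, and order is randomised and blinded. The SAP plans no adverse event comparison in any case.

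Nor is it right that the active-first group is observed for eight weeks. Its one laboratory and ECG come 28 half-lives after the active study day, on placebo, and say little about the elimination phase.

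Two possible illustrations are weaker than they look. Section 7.0 records "There has been skin irritation at the site of ECG lead placement during GSK2256294", with no statement of delayed onset. And no text says that the birth-control requirement stops on day 7; the documents are silent on when it ends.

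Finally, some pages are absent from the public copy, including consent material, so a follow-up schedule there cannot be excluded.

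**Conclusion.** The point holds as a gap in safety ascertainment. As written, the plan schedules no safety assessment after day 7 of period 2, when about 37–42% of active-drug exposure is still to come. That range rests on the stated half-life, linear kinetics and a check 4 to 12 hours after the seventh dose. About 17 of 34 subjects are affected on active drug, if allocation is 1:1. All 34 lack a scheduled check for late biopsy-site complications after their second study day. The 16.2% versus 8.4% limits are illustrative, and somewhat generous to the plan, because the one check that the active-first group does have comes late.

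The consequence is incomplete, order-dependent capture of late events, with no rule for which treatment an event in washout belongs to. This is a cheap improvement to the plan, not a threat to its main conclusion.

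**What to change.** Amend sections 6.0 and 8.0 as follows:

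- Add one telephone contact in each period, at the same interval after the last dose, using the questionnaire already named in section 7.0.
- State that adverse events are counted per treatment from first dose to that contact, so the windows are equal in both periods and both orders.
- State how events reported later in washout are attributed.
- State whether the pregnancy-testing and birth-control provisions of section 4.0 cover the time after period 2.

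The length of the interval is for the sponsor and investigator to set in light of the stated half-life, as is the content of any pregnancy or contraception provision.

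The cost is a protocol amendment, two short calls per subject (2 × 34 = 68 calls if all complete) and slightly longer participation after period 2. No new instrument or procedure is needed.

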In vivo, EETs can enhance insulin sensitivity not only through direct effects on insulin signaling, but also by increasing blood flow and insulin and glucose delivery. In wild-type and obese insulin-resistant mice (db/db), administration of an sEH inhibitor increases muscle capillary blood volume and microvascular blood flow as measured by contrast-enhanced ultrasound; in db/db mice this is accompanied by a decrease in glucose.²² Conversely, insulin-induced increases in muscle capillary blood volume and microvascular blood flow are prevented by administration of an epoxygenase inhibitor.²²

EETs or sEH inhibition may enhance insulin secretion. Studies in islets provide conflicting data regarding the effect of EETs on insulin release.³⁹⁻⁴¹ Luo et al. reported that Ephx2-null mice and sEH inhibitor-treated mice demonstrate preserved glucose-stimulated insulin secretion and are protected against islet cell apoptosis following STZ treatment.^{24,25} Insulin release in response to glucose or potassium channel inhibition is increased in isolated islets from Ephx2-null mice and mice treated with an sEH inhibitor.²⁴ EETs may also influence pancreatic islet cell number or size in models of T2DM. In HF-fed mice, for example, targeted deletion of Ephx2 or selective sEH inhibition increases islet size and vascular density measured by staining for CD31.¹⁹ Other investigators report that sEH inhibition increases the number of β cells without increasing islet size in high carbohydrate- and HF-fed rats.²⁰ *We have not observed an effect of EPHX2 genotype on glucose-stimulated insulin*

secretion in humans, and for this reason focus this proposal on insulin sensitivity.

[figure not shown]

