Studies in rodents point to an important role for EETs and sEH in the regulation of glucose homeostasis and insulin sensitivity (**Figure 2**). Specifically, inhibiting sEH or disrupting *Ephx2*, the gene encoding *sEH*, increases insulin sensitivity in rodent models of T2DM and insulin resistance. These effects have been attributed to enhanced insulin signaling in liver, muscle, and adipose tissue, as well as to beneficial effects on muscle capillary blood volume and microvascular blood flow. Administration of exogenous EETs replicates these effects. Other studies have identified a beneficial effect of EETs or sEH inhibition on islet cell function or apoptosis. Unfortunately, studies in rodents also suggest that tissue sEH activity increases with obesity.

Our group has begun to elucidate the role of EETs and *EPHX2* in the regulation of glucose homeostasis in humans. We have found that circulating EETs correlate with insulin sensitivity and are significantly decreased in individuals with insulin resistance.²⁸ In addition, we have found that insulin sensitivity is increased in overweight carriers of a loss-of-function variant in *EPHX2* (rs751141 or Arg287Gln), but not in obese carriers of the variant.²⁸ The 287Gln allele is also associated with decreased vascular resistance.²⁹ We propose to study the mechanism of these effects and to test *the overarching hypothesis that genetic or*

pharmacological factors that decrease sEH activity will improve insulin sensitivity by increasing blood flow and/or by increasing tissue insulin signaling. We will test the hypothesis that treatment with a specific sEH inhibitor decreases sEH activity and increases insulin-stimulated vasodilation and insulin sensitivity, via effects on tissue (muscle or adipose) insulin signaling and/or increased microvasculature.

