Soluble Epoxide Hydrolase Inhibition and Insulin Resistance NCT03486223

Statistical Analysis plan from IRB approved version dated Date 8/11/2021

Statistical Analysis Plan:

The primary analysis will focus on the effect of GSK2256294 versus placebo on insulin sensitivity. Secondary endpoints will include the effect of GSK2256294 on insulin-stimulated FBF and renal blood flow; insulin-stimulated AKT phosphorylation in muscle and adipose tissue; tissue CD31 and VEGF expression; insulin-stimulated suppression of hepatic glucose production; plasma, muscle, adipose tissue sEH activity and EETs; and tissue and circulating adipokines and cytokines.

Sample Size and Power Calculation: In our prior study of the relationship between EPHX2 Arg287GIn genotype and insulin sensitivity in obese individuals the insulin sensitivity index was 8.24±4.6 mg/kg/min per μ U/mL*100 (mean±SD) in carriers of the 287GIn allele versus 3.54±1.3 mg/kg/min per μ U/mL*100 in Arg/Arg homozygotes. Conservatively assuming a correlation of 0.5 between two measures of insulin sensitivity in the same subject, the study can detect a within-subject difference of 3.76 (80% of the above difference) or larger (with an SD for the within-subject difference of 4.6) with 80% power and 0.05 type 1 error rate with 34 subjects. The sample size was chosen to allow us to detect effects of treatment within racial or gender group. We need 16 per group to have 86% power to detect difference in insulin sensitivity noted above. Moreover, with 34 subjects, we have 80% power to detect a change in insulin-stimulated FBF of 0.9 mL/min/100 mL in the cross-over study, assuming a within-subject correlation coefficient of 0.5. We will have 80% power to see an increase in insulin signaling (ratio of pAKT to AKT) of 0.07 (0.91±0.13 versus 0.84±0.13 in Arg/Arg).

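### Adipose CD31, which the Protocol treats as a vascular marker, is to be blotted in the adipocyte fraction after the stromal vascular fraction has been spun off

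*Protocol*

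**What the plan says.** Protocol section 6.0, under Laboratory Analyses, has a single entry headed "Western blot analysis of pAKT/AKT, CD31, VEGF". It applies to adipose and muscle samples. For adipose tissue it adds a separation step, a spin of the homogenate at 10,000 g. Of the pellet it says that "the stromal vascular fraction from the pellet at will be recovered"; the wording is damaged at this point. Of the rest it says that "the adipocyte fraction (top of the tube) will be used for Western blots". The antibody list that follows includes CD31 and gives it no different starting material. Each lane carries 30 µg of protein, and Coomassie staining is the loading control for the blots other than pAKT/AKT.

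The SAP, in its opening paragraph, lists "tissue CD31 and VEGF expression" among the secondary endpoints. The Protocol's Background (section 1.0) reports that, in mice fed a high-fat diet, loss or inhibition of sEH "increases islet size and vascular density measured by staining for CD31". The hypothesis in section 2.0 is that the drug acts "via effects on tissue (muscle or adipose) insulin signaling and/or increased microvasculature". On which tissue is available, section 6.0 says: "We will obtain an adipose tissue biopsy (Standard Techniques) and optional muscle tissue biopsy if subject consents".

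**The concern.** The hypothesis has two arms, insulin signalling in tissue and growth of the microvasculature. Taking the adipocyte layer is a sensible choice for the first arm, since it asks about AKT phosphorylation in fat cells. The same choice carries over to CD31, which belongs to the second arm. The plan then separates off the fraction it calls vascular and looks for a vascular marker in what is left.

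At stake is how the adipose CD31 comparison can be read. If it shows no difference between GSK2256294 and placebo, the reader cannot tell an absent microvascular effect from an assay placed on an unsuitable fraction. If it does show a difference, part of that could come from how cleanly the two samples separated. Muscle CD31 does not fully cover the gap, because muscle biopsy depends on separate consent and adipose is the only tissue planned for every subject.

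**Working it through.** The documents give no effect size, SD or power for CD31, so there is no planned figure to reproduce. The check sets the passages side by side.

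1. **Which material is blotted for adipose CD31?** The Western blot entry has one adipose rule, the adipocyte fraction. CD31 is in the heading and in the antibody list, with no exception.
2. **Is the pellet used for anything?** It is said to be recovered, but no assay is named for it.
3. **Is adipose CD31 measured in another way?** No vessel staining or separate CD31 assay is described. The list of uses under Adipose harvest does not mention CD31. It does not mention Western blotting either, so it is not a complete list and its silence is only weak evidence.
4. **What does CD31 stand for in this Protocol?** Vascular density, from the Background. The example there is staining of mouse islets, not a blot of human fat, but it is the only meaning the Protocol gives.
5. **Where are the vascular cells?** By the Protocol's own name for it, in the stromal vascular fraction, that is, in the pellet.

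Steps 1 and 5 conflict for CD31. They do not conflict for pAKT/AKT.

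The consequence for a within-subject comparison can be written without assuming any value. Let V be the CD31 in a sample, c the share of it that stays in the top layer, and P the protein in that layer. At a fixed 30 µg load the lane signal S is proportional to c × V / P. For drug (G) against placebo (0) in one subject:

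ln(S_G / S_0) = ln(V_G / V_0) + ln(c_G / c_0) − ln(P_G / P_0)

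The first term is the quantity of interest. If c and P were the same in both periods, the last two terms would vanish and the proportional change would be preserved, although on a weaker signal. If c differs between spins, the second term adds noise. The third term shows that the result is expressed per unit of adipocyte-layer protein, not per unit of tissue. Nothing in either document measures c or controls it, and neither gives a value for c or for its variability. The size of the loss therefore cannot be computed from the documents.

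**The case against.** The strongest objection is that the key sentence is damaged exactly where it describes the pellet, and that the next sentence speaks of denaturing homogenates, not the adipocyte layer. Perhaps CD31 was always meant for the pellet or for whole homogenate. That is possible, and it is not known whether the damage is in the Protocol or arose when the PDF was read. But the later sentence is general and also covers muscle, which has no separation step, while the adipose rule just before it is explicit. If something else was intended, it still has to be written down.

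Second, the spin is of a homogenate, so some vascular protein may well remain on top. This stands, and it limits the claim. A reader might infer that the adipocyte layer contains no vessel material, that any CD31 signal is an artefact, or that the assay could not show a vascular change. The documents do not support this: they give no data on how CD31 divides between layers, and stable carry-over would cancel from a within-subject ratio. What can be said is that the fraction is depleted. Nor is the vascular material thrown away, since the pellet is recovered.

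Third, CD31 should not be inflated into the trial's one microvascular endpoint. The SAP lists it with VEGF as one item in a long secondary list, does not say which tissue, and gives no decision rule for it. Forearm and renal blood flow also bear on the vascular mechanism, although neither measures vessels in fat.

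Finally, a reader might extend the criticism to VEGF. Nothing in the documents shows that the adipocyte fraction is wrong for VEGF, so running it on other material would be a preference.

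**Conclusion.** The concern holds for adipose CD31 only. As written, that part of a named secondary endpoint would be measured in a fraction that the Protocol's own terms imply is depleted of vascular cells. This is a stated rule that does not suit one of the proteins it covers, and so more than a missing detail. A null adipose result would say little about adipose microvasculature, and carry-over that differs between spins could add noise.

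The conclusion rests on two readings: that the adipose rule applies to CD31 because no exception is given, and that the fraction's name describes its content. Neither the degree of depletion nor the variation in carry-over is quantified in the documents, so no size is attached to the loss. As planned, it would touch the adipose CD31 data of all 34 subjects in both periods. Muscle CD31, pAKT/AKT, the primary insulin-sensitivity analysis and the sample size are unaffected.

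**What to change.** Repair the damaged sentence and say which adipose material goes with which protein. Keep the adipocyte fraction for pAKT/AKT. For CD31, name one of two sources:

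- **The stromal vascular pellet**, which the procedure already recovers. The result is then CD31 per unit of pellet protein and should be described that way.
- **Unfractionated adipose homogenate**, as is done for muscle. This is closest to the SAP's wording of a tissue-level endpoint, but an aliquot has to be kept back before the spin. For samples already separated, only the pellet would remain.

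Use the same source for every subject and both periods, and state it beside the CD31 endpoint in the SAP. No change to VEGF is required, though the entry should say which fraction it comes from.

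The cost is a sentence in the laboratory section and an extra set of lanes, with no new biopsy, visit or subject burden. The one practical risk is protein yield: whether the pellet can supply the 30 µg load should be checked before committing to it.
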